9.1 FREQUENCY

9.2 SAMPLING PLAN

9.3 MONITORING TASKS

9.4 STUDY CLOSE-OUT

**10. ETHICAL AND REGULATORY REQUIREMENTS**

9.1 CODE OF CONDUCT

9.2 INSTITUTIONAL REVIEW BORDS/ETHICS COMMITTEE

9.3 INFORMED CONSENT

9.4 SUBJECT CONFIDENTIALITY

## STUDY SUMMARY

TITLE	Prospective Single-Center Study on E1 Acetabular liner in THA
DESIGN	Prospective Observational Study
PURPOSE	Evaluate E1 wear, Clinical Performance of E1 liner in THA in Korean Patient Population
OUTCOME MEASURES	Clinical Outcomes (e.g. HHS, EQ5D, UCLA), Radiographic Assessment and Survivorship
POPULATION	100
ELIGIBILITY	Approved Indications for Uses for E1 liner in THA
DURATION	All cases will be followed up to 10 years. It is expected that the enrolment will be completed in 1 year; the total duration of the study is 11 years.

CONFIDENTIAL

## 1. INTRODUCTION

### 1.1. BACKGROUND

Total hip arthroplasty (THA) is one of the most successful surgical procedures in general. Yet, a few problems remain unsolved, and aseptic loosening is probably the most important of them. One of the main reasons for aseptic loosening in THA is the foreign body reaction caused by the wear particles. Since the late 1990s, the orthopedic industry has been developing highly crosslinked polyethylene (HXLPE) materials to capitalize on the increased wear resistance. In 2007, E1® Antioxidant Infused Technology was developed to reduce wear rate, maintain mechanical properties and prevent oxidative degradation.

Also alumina ceramic was introduced as a bearing surface in the 1971 as an alternative to the metal on-polyethylene couplings. Since then, alumina ceramic has been used in THA successfully for more than 35 years. BIOLOX®Delta is designed with improved fracture toughness, further reduces the risk of fracture and also extends the design flexibility of the material.

However, there are a few clinical data collected on wear and performance of E1® Liners available for Caucasian population and no data for Koreans today. There is no clinical data of BIOLOX®Delta femoral head articulating against E1® Liner. Therefore, it is needed to collect clinical data to support marketing and validate design of E1® Liners in terms of its safety and efficacy.

### 1.2. DEVICE DESIGN AND DESCRIPTION

Vitamin E doping of highly cross-linked polyethylene is a proposed method for insuring long-term oxidative stability of highly cross-linked ultra-high molecular weight polyethylene for use in total joint arthroplasty. In vitro research and development studies have shown that this material has improved wear performance, retention of mechanical properties, and a high resistance to oxidation due to the anti-oxidative properties of Vitamin E.

All patients will receive the vitamin E treated polyethylene “E1® Liners”. Short-term femoral head penetration and long-term steady state wear of the polyethylene will be measured using software.

- E1® Acetabular Liners: flat (MaxRom, MaxRom+).
- BIOLOX®Delta femoral heads: used for the investigational cohort. The BIOLOX® Delta ceramic femoral heads are manufactured from BIOLOX® delta, an alumina composite matrix
- Taperloc Complete Hip Stem.
- RingLoc® Universal Acetabular Shell System.

### 1.3. RATIONALE FOR CURRENT STUDY

It is important to conduct a detailed clinical follow-up study when materials or implant designs are introduced for clinical use. Validated patient administered questionnaires allow for functional assessment, patient satisfaction and cost effectiveness analysis. These well established assessment techniques are well suited for evaluating large patient populations.

### 1.4. PURPOSES

A PROSPECTIVE SINGLE-CENTER STUDY ON E1 ACETABULAR LINER IN THA

The purpose of the study is to evaluate clinical performance of E1 liner in THA in Korean patient population.. The clinical performance will be evaluated based on patient outcomes, radiographic assessment and survivorship.

## 2. STUDY DESIGN

### 2.1. OVERALL DESIGN

This study will be a single-center observational study on patients received E1 liner in THA. Patient demographic, preoperative clinical outcomes and operative information will be collected prospectively per defined follow-up intervals.

### 2.2. NUMBER OF SITES AND SUBJECTS/PROCEDURES

There is one site in Korea to participate in this study.

### 2.3. EFFICACY AND/OR SAFETY HYPOTHESES

Not applicable as this is a Post Market Study.

### 2.4. PRIMARY AND SECONDARY ENDPOINTS

Primary endpoint is HHS score at 1 year follow-up.

Secondary endpoints include

- HHS at other follow-up visits
- EQ5D, UCLA at 6month, 1 year, 2 year, 5 year postop
- Radiographic Assessment at Immediate post-op, 6 months, 1 year, 2 year, 5 year postop
- Survivorship up to 10 years

### 2.5. ASSESSMENT PROCEDURE

#### 2.5.1. ASSESSMENT PARAMETERS AND METHODS

##### Medical History and Demographic Data

Demographic information will be collected which will include but is not limited to gender, age at surgery, height, weight, primary diagnosis & medical history

##### Clinical Assessments

Clinical assessments will include functional scores, radiographic analysis.

An operative record will be completed upon the surgery. The operative record will include but are not restricted to date of surgery, surgical approach, implant components (part number).

A PROSPECTIVE SINGLE-CENTER STUDY ON E1 ACETABULAR LINER IN THA

Radiographic Assessments

Radiographic assessments including polyethylene wear analysis and cup inclination angle will be completed at each follow-up period.

The X-rays must be taken which requires an A/P pelvis view centered over the pubis. For the polyethylene wear analysis, all Radiographic images will be determined and the penetration rate will be measured by an independent analyst. (PolyWare pro 3D distal version 7.02 software)

**2.5.2. ASEESMENT TIMELINES/SCHEDULE**

Clinical and Radiographic Exams									
Data Collection item	Pre-operative	Intra-operative	Immediate Post-operative	6 Months	1 Year	2years	5 years	7 years	10 years
Demographic and Medical History	X								
Operative Record		X							
Clinical Evaluation – HHS, EQ5D, UCLA	X			X	X	X	X		
Radiographic assessment			X	X	X	X	X		X
Wear Analysis				X	X	X	X		X
Phone Interview								X	
Adverse events including revisions	As required								

**2.5.3. ALLOWED WINDOW OF EACH SCHEDULE**

Allowed Window of Each Prospective Visit Schedule:

- 6 months (+/- 1 month)
- 12 months (+/- 3 months)
- 2 years (+/- 3 months)
- 5 years (+/- 3 months)
- 7 years (+/- 3 months)
- 10 years (+/- 3 months)

Each follow-up visit time point will be determined based on the date of surgery.

A PROSPECTIVE SINGLE-CENTER STUDY ON E1 ACETABULAR LINER IN THA

## 2.6. DURATION OF THE STUDY

All cases will be followed up to 10 years. It is expected that the enrollment will be completed in 1 year, the total duration of the study is 11 years.

## 3. SELECTION AND WITHDRAWAL OF SUBJECTS

All subjects, regardless of sex, race, or geographic location, must fit into the scope of the Inclusion/Exclusion criteria to be eligible for the study. If required per applicable regulations, all participants must sign an Informed Consent to be enrolled into the study.

### 3.1 INCLUSION CRITERIA

Patients will be included in this study if they received Ringloc acetabular system with E1 liner per the approved indications for use by KFDA in Korea. Specifically,

- a. Osteoarthritis
- b. Avascular necrosis
- c. Legg Perthes
- d. Rheumatoid Arthritis
- e. Diastrophic variant
- f. Fracture of the pelvis
- g. Fused hip
- h. Slipped capital epiphysis
- i. Subcapital fractures
- j. Traumatic arthritis

Patients aged over 20

Patients with limited co-morbidity – ASA I – III

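### Do the inclusion criteria need to require the BIOLOX Delta head, given that missing data on that head with the E1 liner is part of the rationale?

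*Combined protocol and SAP*

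**What the plan says.** Section 1.1 gives two gaps in the evidence. The first concerns the population: "there are a few clinical data collected on wear and performance of E1® Liners available for Caucasian population and no data for Koreans today". The second concerns the bearing couple: "There is no clinical data of BIOLOX®Delta femoral head articulating against E1® Liner". The conclusion drawn from them is about the liner: "it is needed to collect clinical data to support marketing and validate design of E1® Liners in terms of its safety and efficacy".

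Section 1.2 lists the devices: the E1 liner, one femoral head, one stem and one shell. The head entry reads "BIOLOX®Delta femoral heads: used for the investigational cohort". That cohort is not defined, and no second cohort is described. The one component stated for everyone is the liner: "All patients will receive the vitamin E treated polyethylene".

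The Study Summary and section 1.4 give the purpose as the performance of the E1 liner in Korean patients. Section 2.1 describes a "single-center observational study on patients received E1 liner in THA". Section 3.1 admits patients as follows: "Patients will be included in this study if they received Ringloc acetabular system with E1 liner". The exclusion criteria in section 3.2 do not mention the head. Section 2.5.1 has the implant components recorded by part number. Section 6.3 lists five analyses, none of them by head type.

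**The concern.** Section 1.1 presents the Delta/E1 couple as unstudied, yet section 3.1 does not require a Delta head. The cohort label in section 1.2 could even suggest a second group with a different head. Read literally, a patient with an E1 liner and any other head is eligible and goes into the same analyses.

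For wear and long-term survivorship this could matter. Penetration of the head into the polyethylene depends on both surfaces. If heads were mixed, a pooled 10-year result would describe whatever mix the surgeon happened to use, and could not be attributed to the Delta/E1 couple. One of the two gaps behind an 11-year study would then be only partly filled.

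**Working it through.** **1. Does eligibility match the purpose?** The conclusion of section 1.1, the Study Summary, section 1.4 and section 2.1 all take the E1 liner as the subject. Section 3.1 selects on that liner and its shell. The rule is therefore consistent with the stated purpose. It is broader than the second gap in section 1.1, but that gap is not the study's stated objective.

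**2. Is another head foreseen?** Section 1.2 lists one head, BIOLOX Delta. The design has one cohort, so the natural reading is that this cohort is the enrolled one. Other bearing materials appear only in the general background and in the package-insert text of section 11. The document gives no share of other heads.

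**3. Does the primary analysis depend on the head?** Inputs from section 6.1: two-sided alpha 0.05, power 0.90, difference 5 HHS points, SD of paired differences 15.16.

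- Normal approximation: n = (15.16 × (1.960 + 1.2816) / 5)² = 96.6, so 97.
- Exact noncentral t: power 0.898 at n = 98, 0.901 at n = 99 and 0.904 at n = 100.

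The plan's N = 99 is reproduced exactly, and no input involves the femoral head.

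**4. What would a mix cost?** The shares below are assumptions, for illustration only. Survivorship is assumed to be 95%, censoring is ignored, and half-width = 1.96 × √(0.95 × 0.05 / n).

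| Patients with a Delta head (of 100) | 95% half-width, survivorship (points) | Power for a 5-point HHS change in that subset |
|---|---|---|
| 100 | 4.27 | 0.90 |
| 80 | 4.78 | 0.83 |
| 60 | 5.51 | not computed |
| 50 | 6.04 | 0.63 |

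At 50 patients the interval is wider by 6.04 − 4.27 = 1.77 points. With 50 × 0.05 = 2.5 expected revisions the normal interval is rough, so that row shows only the order of size. The power column applies only if the HHS test were confined to the Delta subset, which the plan does not propose.

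**5. Would the mix be hidden?** No. Part numbers identify the head for each patient, so head type can be tabulated and survivorship split at any report. No comparison between heads is planned, so no planned estimate is a head effect that patient selection could confound. Section 6.3 also lists no wear analysis, so the plan does not commit to a pooled wear result.

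**The case for a change.** The strongest counter-argument is that repair is cheap and the text is unclear whichever way the heads were used. If every patient receives a Delta head, the protocol should say so, and readers could then attribute the results to that couple. If not, the split should be fixed in advance. The Study Summary puts wear first in the purpose, and section 2.5.2 schedules wear analysis from 6 months to 10 years. Attribution to the couple is therefore not a side issue.

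Part of this stands. The cohort label in section 1.2 is undefined, and section 3.1 does not carry over the head that section 1.2 names. A sentence clarifying both would read better.

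It does not follow that the results are at risk. Making the Delta/E1 subset primary for wear and survivorship would narrow the stated purpose from the liner to one couple. That is a choice about scope and does not correct an error. Pre-specifying a report by head changes nothing unless other heads are used. If they are, an analyst who sees more than one head type among the part numbers would describe the mix and show survivorship by head without being told to.

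**Conclusion.** The wording mismatch between sections 1.2 and 3.1 is genuine but minor, and no change to the plan follows. Followed as written, the plan gives sound results for its stated purpose and primary endpoint: eligibility fits the E1-liner objective, and HHS at 1 year and N = 99 are untouched by head type. Any mix of heads can be recovered from data already collected. Under the most extreme share considered, half the patients, the loss for the Delta subset is about 1.8 points of half-width on survivorship.

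This rests on two assumptions: that Delta, the only head listed, is the head generally used, and that the recorded part numbers include the head. If a substantial share of patients turned out to have other heads, survivorship, and wear where analysed, should be read by head before any statement is made about the Delta/E1 couple. That is ordinary care in reporting and needs no amendment now.

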### 3.2 EXCLUSION CRITERIA

Exclusion Criteria for this study should comply with the stated contraindications on package inserts of Ringloc acetabular system with E1 liner. These indications are stated below:

Absolute contraindications include: infection, sepsis, and osteomyelitis

Relative contraindications include:

- 1) uncooperative patient or patient with neurologic disorders who are incapable of following directions,
- 2) osteoporosis,
- 3) metabolic disorders which may impair bone formation,
- 4) osteomalacia,
- 5) distant foci of infections which may spread to the implant site,
- 6) rapid joint destruction, marked bone loss or bone resorption apparent on roentgenogram, and
- 7) vascular insufficiency, muscular atrophy, or neuromuscular disease.
- 8) pregnancy

A PROSPECTIVE SINGLE-CENTER STUDY ON E1 ACETABULAR LINER IN THA

### 3.3. SUBJECT WITHDRAWAL

It is recognized that the subject's participation in this trial is entirely voluntary, and that she/he may refuse to participate and may withdraw from participation at any time without jeopardy to any future medical care. It is also recognized that the investigator, at his/her discretion, may withdraw a subject from this study based upon his/her professional judgment. In event of subject withdrawal, applicable local procedures should be followed

## 4. PROTOCOL DEVIATION MANAGEMENT AND REPORTING

Protocol deviations are unplanned and unintentional events. Any changes in the research protocol during the period, for which IRB approval has already been given, may not be initiated without submission of an amendment for IRB review and approval.

In any protocol deviations occur during the trial will be reported to any necessary institutions to manage. And that information also be reported to IRB and sponsor.

## 5. ADVERSE EVENT MANAGEMENT AND REPORTING

A record of all adverse events, including details of the nature, onset, duration, severity, relationship to the device, relationship to the operative procedure and outcome, will be made and provide to the study sponsor. The subject will be questioned about any adverse event(s) at each subsequent follow-up assessment visit.

## 6. STATISTICAL ANALYSIS PLAN

### 6.1 SAMPLE SIZE CALCULATION

The primary objective of this study is to show that there is a significant increase in Harris Hip Scores from baseline to 1 year post-surgery. The hypothesis can be stated as follows:

$$H_0: \mu_d = 0 \quad \text{vs.} \quad H_A: \mu_d \neq 0,$$

Where  $\mu_d$  = the mean of the paired differences ( $HHS_{1\text{Year}} - HHS_{\text{preop}}$ ).

This hypothesis will be tested using a paired t-test of mean difference equal to zero.

Harris Hip Score difference of **4 points** was shown to be the best cutoff point for optimal sensitivity and specificity to detect clinical improvement (Hoeskma et al. Ann Rheum Dis 2003; 62: 935–938).

If we choose to detect a least clinical acceptable difference in Harris Hip Score of **5 points** with the following assumptions:

$\alpha = 0.05$	Probability of Type I Error
$\beta = 0.10$	Probability of Type II Error
$s_d = 15.16$	Estimated standard deviation of the differences (based on Biomet previous Arcom and ArcomXL study)

Sample size required is N= 99 rounds to 100 subjects.

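### Is the primary HHS test flawed because it tests against zero change although the plan names thresholds of 4 and 5 points?

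*Combined protocol and SAP*

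**What the plan says.** Section 6.1 sets as the primary aim a statistically significant rise in HHS between the preoperative assessment and the 1-year visit. The null is a mean paired difference of zero with a two-sided alternative, and the method follows: "This hypothesis will be tested using a paired t-test of mean difference equal to zero".

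Two clinical figures appear in the same section. A difference of 4 points, taken from a cited study, "was shown to be the best cutoff point for optimal sensitivity and specificity to detect clinical improvement". The sample size then rests on a second figure, 5 points, introduced with the words "If we choose to detect a least clinical acceptable difference in Harris Hip Score of". Its other inputs are α = 0.05, β = 0.10 and an SD of the paired differences of 15.16. The result is N = 99, rounded to 100.

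No other section attaches a threshold to the primary result. Section 2.3 declares efficacy and safety hypotheses not applicable because the study is post-market. Section 1.4 gives the purpose as evaluating clinical performance from patient outcomes, radiographs and survivorship. Section 6.3 lists the mean HHS at 1 year and comparisons of preoperative with postoperative scores.

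**The concern.** The 5-point figure is described as the least acceptable difference, yet it enters only the sample-size formula. The 4-point figure enters no analysis at all. The test asks only whether the mean change differs from zero, and the study has no control arm. A mean gain too small to count as improvement by the plan's own figures could therefore be statistically significant.

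If a significant p-value were then presented as proof of clinically acceptable performance, the claim would go further than the evidence. Section 1.1 speaks of collecting data to support marketing and to validate the design, so the question is a fair one. It is also true that power at 4 points is below the 90% quoted for 5.

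**Working it through.** **Inputs, all from section 6.1:** SD of the paired differences 15.16; two-sided α = 0.05; power 0.90; design difference 5; N = 99, rounded to 100.

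**1. The plan's sample size.** Normal approximation: n = [(1.960 + 1.2816) × 15.16 / 5]² = 96.6, so 97. The exact paired t-test (noncentral t) needs N = 99, with power 0.901; at N = 100 power is 0.904. The stated figure reproduces. One-sided versions give 79 (normal) or 81 (t) and do not.

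**2. The smallest significant gain.** SE = 15.16 / √100 = 1.516, and t(0.975, 99 df) = 1.9842. The boundary is 1.9842 × 1.516 = 3.008 points. A gain of exactly 3.00 just misses (t = 1.979, p = 0.0506). A gain of 3.01 gives p = 0.0499 and a 95% CI of 0.002 to 6.02. The boundary depends on the observed SD; for illustrative SDs of 12, 18 and 20 it is 2.38, 3.57 and 3.97.

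**3. Why the boundary lies below 5.** In the normal approximation, the ratio of the significance boundary to the design difference is z(α/2) / [z(α/2) + z(β)] = 1.960 / 3.2416 = 0.605. It depends only on α and power. Any trial powered at 90% with a two-sided 5% test reaches significance at about 60% of its design difference; here 0.605 × 5 = 3.02. The boundary of about 3 is thus the ordinary consequence of powering at 5.

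**4. Power at other true gains, and the alternative null.** With the same SD and N, power against a null of 5 at a true gain of g equals power against zero at g − 5. One calculation therefore fills both columns (N = 100):

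| Points above the null | Power | True gain if null = 0 | True gain if null = 5 |
|---|---|---|---|
| 1 | 10% | 1 | 6 |
| 2 | 26% | 2 | 7 |
| 3 | 50% | 3 | 8 |
| 4 | 74% | 4 | 9 |
| 5 | 90% | 5 | 10 |

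Power at a true gain of 4 points is indeed 74% under the plan, but the plan claims 90% at 5 points only, and there the figure is right.

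For the lower 95% limit to exceed 5, the observed mean must exceed 5 + 3.008 = 8.01. A true gain of exactly 5, the plan's own least acceptable difference, would pass 2.5% of the time. For 90% power against a null of 5, a true gain of 9 needs 153 patients and a true gain of 8 needs 271. N = 100 is enough only if the true gain is about 10 or more, and the documents give no expected gain.

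**5. The wording of section 6.1.** The objective (a significant increase), the null (zero), the test (paired t against zero) and the power statement (90% at 5 points) fit together. None of them says that a significant result shows a gain of at least 4 or 5.

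**The case for a change.** The best argument for the concern is that power at 5 points does not turn a significant result into evidence of 5 points. In a single-arm study, the plan's own benchmarks are almost all that could give the pre-post change clinical meaning. If gains after hip replacement are large, a null of zero tells the reader little, and a stricter null would be cheap: against 5, power is 90% at a true gain of 10 and above 99.9% at 15.

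The first part stands as a rule for reading the result: rejecting zero shows an increase and no more. But the plan claims no more, so there is no statement to correct. The second part rests on an assumed gain that the documents do not supply. With gains of 15 or more, both tests reject almost surely and the conclusion that scores rose does not change. With gains of 6 to 9, the stricter test would often fail although the true mean exceeds the least acceptable difference.

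The 4-point figure gives little support. It is described through sensitivity and specificity, which suggests a cutoff for classifying individual patients and not a bar for a group mean. A proportion of patients improving by 4 points or more would be a reasonable optional addition, but it would leave the primary result as it is. A confidence interval for the mean change is routine reporting and lets any reader compare the gain with 4 and 5.

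**Conclusion.** The concern does not hold. Its arithmetic is essentially right: at N = 100 and SD 15.16 the boundary is 3.008 points, and power is 50%, 74% and 90% at true gains of 3, 4 and 5. These figures describe a conventional design: test against no change, with the sample size chosen to detect a relevant difference. Section 6.1 is consistent on this point, and its N is correct.

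Replacing the null by 5 points would be a preference for superiority by a margin. It would move the observed bar from about 3.0 to about 8.0, and N = 100 would suffice only on an assumed true gain of about 10 or more.

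This conclusion assumes that the observed SD is near 15.16, that about 100 patients are analysed, and that a significant test is reported as what section 6.1 sets out to show, an increase from baseline.

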## **6.2 HANDLING OF MISSING AND INCOMPLETE DATA**

Attempt will be made to ensure that patients come back for scheduled follow-up evaluations. In case of missing data, for clinical outcome scores, Last Observation Carried Forward will be used to impute the missing data. For survivorship analysis, the data including implant in situ collected in the next follow-up will be used to calculate survivorship

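### Does enrolling 100 patients leave the study short of its stated 90% power, because 6.1 makes no allowance for loss and cites a 4-point cutoff?

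*Combined protocol and SAP*

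**What the plan says.** Section 6.1 sets the primary test: "This hypothesis will be tested using a paired t-test of mean difference equal to zero", where the difference is the 1-year HHS minus the preoperative HHS. The alternative is two-sided, alpha is 0.05, beta is 0.10, and the standard deviation of the differences is 15.16, taken from earlier studies by the sponsor. The result is: "Sample size required is N= 99 rounds to 100 subjects". The Study Summary also gives a population of 100.

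On the effect size, 6.1 first cites a published responsiveness result: "Harris Hip Score difference of 4 points was shown to be the best cutoff point for optimal sensitivity and specificity to detect clinical improvement". The next sentence begins: "If we choose to detect a least clinical acceptable difference in Harris Hip Score of 5 points". No reason is given for moving from 4 to 5.

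On missing data, 6.2 opens: "Attempt will be made to ensure that patients come back for scheduled follow-up evaluations". It then prescribes LOCF for clinical scores that are nevertheless missing. Section 3.3 allows withdrawal at any time. The schedule in 2.5.2 collects HHS before surgery, at 6 months and at 1 year, so a postoperative score is due before the primary time point. No section gives an expected loss rate.

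**The concern.** The figure of 99 counts complete pairs, while 100 is the number enrolled. The one spare patient comes from rounding up and was not planned as a margin for loss. Read as a complete-case design, the second unusable pair takes power below the stated 90%, although the plan itself provides for withdrawal and missing scores.

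The effect size raises a second doubt. A reader who takes the cited 4 points as the smallest change that matters might suppose that the study has 90% power for it. It has not. Describing 5 points as the least acceptable difference, immediately after citing 4, invites that misreading. If the primary test came out null or borderline, the result would then be judged against a power higher than the study had for the effect the reader had in mind.

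**Working it through.** **Inputs (6.1).** Two-sided alpha 0.05; beta 0.10; difference δ = 5; standard deviation s = 15.16; one cohort, paired t-test against zero.

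**The plan's own figure.** The normal approximation is n = [s(z₀.₉₇₅ + z₀.₉₀)/δ]² = [15.16 × (1.960 + 1.282)/5]² = 96.6, so 97. The exact calculation uses a noncentral t with n − 1 degrees of freedom and noncentrality δ√n/s. At n = 99 the noncentrality is 5 × √99/15.16 = 3.28 and power is 90.1%; at n = 98 power is 89.8%. The smallest n that reaches 90% is therefore 99, as stated. At n = 100 power is 90.4%.

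**Complete pairs only, for reference.**

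| Pairs | Power at 5 points | Power at 4 points |
|---|---|---|
| 100 | 90.4% | 74.3% |
| 98 | 89.8% | 73.4% |
| 95 | 88.9% | 72.1% |
| 90 | 87.2% | 69.7% |
| 80 | 83.0% | 64.5% |
| 75 | 80.5% | 61.6% |

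For 90% power at 4 points, 153 pairs would be needed.

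**Under the plan's LOCF rule.** All 100 patients stay in the analysis, so the complete-pair rows do not describe it. Let m be the share with no 1-year score (assumed, since the documents give no rate). Take the true 1-year mean change as 5 and assume that missingness is unrelated to outcome.

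- *Preoperative score carried forward*, so those changes are zero. The mean is 5(1 − m) and the variance is (1 − m)s² + m(1 − m)5². At m = 0.10 the mean is 4.5, the SD is √(0.9 × 15.16² + 0.09 × 25) = 14.46, and power is 86.9%. At m = 0.20 the mean is 4.0, the SD is 13.71, and power is 82.4%.
- *6-month score carried forward, 6-month gain equal to the 1-year gain, same SD*. The mean stays at 5 and power stays at 90.4% for any m.
- *6-month score carried forward, 6-month gain 80% of the 1-year gain, same SD within each group*. At m = 0.10 the mean is 0.9 × 5 + 0.1 × 4 = 4.9 and power is 89.3%. At m = 0.20 the mean is 4.8 and power is 88.0%.

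The documents do not give the 6-month gain, so the last two cases are illustrations. At 10% missing, power runs from about 87% to 90.4% across these cases. The lower end requires that none of the missing patients was seen at 6 months.

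**Larger effects.** The documents give no expected change. If it were 6 points, 90 complete pairs would give 96% power; at 7 points, 99%. At 10 points, even 50 pairs would give more than 99%.

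**The case for a change.** The strongest case for acting is that 6.1 is the only justification for the sample size, and that its power figure holds for the enrolled number only if the 1-year data are nearly complete. LOCF does not restore the figure for a patient with no postoperative score: a change of zero costs about as much power as dropping the pair (86.9% against 87.2% at 10%). The step from 4 to 5 points matters numerically, 74% against 90%, and no reason is given for it. Two sentences would put both right at no cost in patients.

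The facts in this stand; the conclusion that the plan must change does not. The LOCF argument covers only patients missed at both 6 months and 1 year. Anyone seen at 6 months contributes that score, so one cannot say in general that a second loss misses the target. The 4-point value is described as a cutoff that "was shown to be the best cutoff point for optimal sensitivity and specificity to detect clinical improvement". A cutoff of that kind need not be the mean change a study is powered to detect, and the test here is against zero. The plan claims 90% for 5 points only. Restating 6.1 in terms of 90 evaluable pairs would also sit badly with 6.2, which imputes and does not drop patients, and it would write an invented loss rate into the protocol.

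**Conclusion.** No change follows. The sample size is correct on its own inputs, and 100 patients deliver the stated power for the stated 5-point difference when 1-year data are complete. With 10% missing, power under LOCF is between about 87% and 90%, a shortfall of at most about 3 percentage points. Even as a complete-case analysis, power for 5 points stays above 80% down to 75 pairs, a loss of 25%. These figures rest on an SD of 15.16, a true mean change of 5, missingness unrelated to outcome, and loss rates that the documents do not supply.

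Two explanations are absent: that the 90% presumes nearly complete 1-year scores, and why 5 points is called the least acceptable difference beside a cited 4. An analyst can supply the first from 6.1 and 6.2 and can treat 74% at 4 points as a sensitivity figure. Adding either sentence would alter no enrolment target, test or estimate. Whether LOCF is a good imputation rule is a separate question, which this point does not decide.
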